6.5.1 Protection Against Risks

General Risks of Study Protocol and Procedures

Data collected will include a review of the air medical patient care report(s), Emergency Department and electronic/ paper hospital records. Prehospital Data: Demographics, air medical response times (call receipt to arrival, arrival at patient side,) injury characteristics, vital signs, prehospital resuscitation volumes, prehospital interventions (needle decompression, chest tubes)

referring hospital vitals, and interventions will be recorded. In-Hospital Data: Demographics, shock severity (base deficit, lactate), injury characteristics, ED vitals, ED interventions (chest tubes, intubation), injury severity, operative interventions and timing of interventions, injury severity score, ICU days, ventilator days, length of stay, multiple organ dysfunction scores (daily), nosocomial infectious outcomes, blood gas results, chest x-ray reads, transfusion of blood and blood components, resuscitation requirements, all primary and secondary outcomes will be recorded.

Data Entry and Storage: MACRO and associated internet technology affiliates at the University of Pittsburgh will create web-based data entry platform to collect necessary information for the proposed pilot study.

All research interventions/activities will be conducted in private patient care areas. The collection of sensitive information about subjects is limited to the amount necessary to achieve the aims of the research, so that no unneeded sensitive information is being collected.

A Case Report Form will be completed for each subject enrolled into the clinical study. The Investigator will attest that all clinical and laboratory data entered on the CRF are complete, accurate and authentic using a signoff page within the data entry platform. A key linking the subject to the code number will be kept locked in a secure location and will be available only to the investigators. The data and samples will be retained indefinitely and used for future testing. Data from this study, without the subject's identity, may be reported in scientific meetings, articles or other appropriate communications.

The Investigator will retain the data for the entire period of this study and will retain the specified records and reports for a minimum of 7 years after completion of the study. Subject names or other directly identifiable information will not appear on any reports, publications, or other disclosures of clinical study outcomes.

6.5.2 Protection Against Potential Risks of Experimental Intervention

MACRO research coordinators for the pilot trial will document and verify all trauma arrivals via air medical transport for PPOWER enrollment. Those patients who met inclusion and exclusion criteria during air medical transport that were enrolled will be verified and those patients will undergo initial laboratory and blood sampling within the first hour of arrival. All requirements for notification for exception from informed consent for emergency research and Title 21, Code of Federal Regulations, Section 50.24 (21 CFR 50.24) will be explicitly followed (Appendix 4).

Training and Participating Site Coordination: As the clinical coordinating center for the proposed pilot trial the University of Pittsburgh will be responsible for all research coordinator training, prehospital provider training and sample collection and storage. Research coordinators, prehospital providers and associated staff will be trained during the months prior to the trial start date regarding the scientific basis for the study, specific inclusion and exclusion criteria, sample collection and processing, prehospital procedures and SOPs, and rapid TEG performance. Trial enrollment and maintenance of data integrity will be assessed monthly using the web-based data platform. Trial screening, enrollment and data completeness and accuracy will be accessed at regular intervals via random patient audit.

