1.2 SPECIFIC AIMS

Hypothesis: The initiation of LTLR-WB resuscitation in the prehospital setting with continuation through the in-hospital acute resuscitation phase of care will significantly reduce the morbidity and mortality attributable to hemorrhagic shock post-injury as compared to standard prehospital and in-hospital resuscitation practice.

Specific Aims:

Specific Aim I: Determine the feasibility and most appropriate study population that will lead to a large multicenter clinical trial designed to evaluate the effectiveness of prehospital through inhospital LTLR-WB as compared to standard care practice in patients at risk of hemorrhagic shock.

Specific Aim II: Determine if prehospital through in-hospital LTLR-WB reduces 28-day mortality, in-hospital mortality, multiple organ dysfunction, presenting coagulopathy, 24-hour resuscitation requirements and early mortality as compared to standard of care prehospital and in-hospital resuscitation in patients at risk of hemorrhagic shock.

Specific Aim III: Determine the primary drivers by which prehospital through in-hospital LTLR-WB improves clinical, resuscitative and hemostatic outcomes as compared to standard of care prehospital and in-hospital resuscitation in patients at risk of hemorrhagic shock.

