2.3 STUDY INTERVENTION

The study intervention will be the initiation of prehospital through in-hospital transfusion of LTLR-WB in patients meeting all inclusion and no exclusion criteria. Whole blood units will be obtained from a local FDA licensed blood center (LifeSource dba Central Blood Bank; Registration number: 2571073; License number: 1025).

Up to two units of LTLR-WB (O+) will be initiated in the prehospital phase of the study with an additional 6 units of LTLR-WB (O+) available during the in-hospital phase of the trial if indicated.

Study Intervention Rationale: To provide the earliest and most robust intervention with appropriate concern for blood banking resource utilization, a prehospital and in-hospital phase intervention will be utilized. As whole blood resuscitation is most pertinent to patients with acute hemorrhage, we have limited the in-hospital acute resuscitation phase time period and the additional 6 units of LTLR-WB to 4 hours post-admission. This acute phase resuscitation period definition is based upon unpublished data from the recently completed PAMPer study at our institution.⁴⁰ Over 79% of the blood products transfused in the first 24 hours occurred in the first 4 hours following admission.

Whole Blood Intervention: Blood from male only, group O+ donors will be collected using the FDA approved Terumo Imuflex® WB-SP blood bag system. With this collection system, whole

blood passes through a platelet sparing inline leukoreduction filter into a bag containing citrate phosphate dextrose solution. Male only whole blood donors will be used in order to mitigate the risk of transfusion related acute lung injury (TRALI; estimated incidence ≈1:12,000). Whole blood collected with this system can be kept as such for up to 21 days when stored between 1-6°C. Per blood bank protocol, the anti-A and anti-B antibody titers in each unit will be tested on a sample from every donor using an immediate spin saline tube method without incubation; only units where the titer of both anti-A and anti-B are <100 will be issued for the study and subsequent transfusion. All other required transmissible disease testing will also be performed on these LTLR-WB units before they are released, as per blood bank standard practice. The LTLR-WB units will have affixed on them the standardized Whole Blood product label thereby making them easily distinguishable from the other non-WB units in inventory.

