Mechanistic Outcomes: The principle factors that may be responsible for beneficial clinical outcome effects associated with or attributable to LTLR-WB resuscitation when initiated early in the prehospital phase of injury are an important and essential objective of the proposed pilot trial. We will compare across treatment arms: 1) Coagulopathy: Coagulopathy will be assessed via PT/PTT/INR and rapid Thromboelastography (r-TEG) measurements. 2) Platelet Function: We will assess platelet activation, aggregation, and adhesion via flow cytometry analysis, whole blood aggregometry measurements and flow chamber analysis under shear stress conditions, respectively in a subset of patients.^{88,89} 3) Glycocalyx integrity: We will assess glycocalyx integrity by measuring serum concentrations of Syndecan-1 and Hyaluronan by ELISA at inhospital time points. 3) Donor Exposure, Age and Volume of Transfusion Products: During the prehospital and in-hospital acute resuscitation phase of the study the number donors from all transfused products blood products, the age of all LTLR-WB and PRBCs from the standard of care arm and overall transfusion volumes will be recorded and compared.

Blood Sampling and In-Hospital Measurements: In-hospital phase blood sampling will occur upon arrival (+ 4 hrs) and at 12 hours (+/- 12hrs) and 24 hours (+/- 12hrs) from time of arrival. Timing of samples will need to be flexible based upon patient availability and logistic factors. This early in-hospital sampling will allow adequate assessment of the benefits of early LTLR-WB resuscitation and appropriate characterization of the proposed clinical and mechanistic outcomes. TEG analysis at arrival, 12hr and 24hr time points will be performed on a TEG[®] 5000 Thromboelastograph[®] Hemostasis Analyzer.

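### The arrival sample has two time limits (1 h and 4 h) and the 12 h and 24 h windows overlap by half, so an arrival value may not be a presenting value

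*Combined protocol and SAP*

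**What the plan says.** Two sections time the first sample:

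- Section 6.5.2, on coordinator verification of patients enrolled during air transport, calls for "initial laboratory and blood sampling within the first hour of arrival".
- Section 2.8, under blood sampling, states "In-hospital phase blood sampling will occur upon arrival (+ 4 hrs", and places the later draws "at 12 hours (+/- 12hrs) and 24 hours (+/- 12hrs) from time of arrival". It adds a reason: "Timing of samples will need to be flexible based upon patient availability and logistic factors".

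The aim that depends on the first sample is in section 1.2, where Specific Aim II lists "presenting coagulopathy, 24-hour resuscitation requirements and early mortality" among its outcomes. Section 2.8 gives the measurement: "Coagulopathy will be assessed via PT/PTT/INR and rapid Thromboelastography (r-TEG) measurements". It ties TEG explicitly to the arrival, 12-hour and 24-hour points.

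On treatment timing, section 2.4 treats the in-hospital acute resuscitation phase as generally the first 4 hours from admission. In that phase the whole blood arm may receive up to 6 further units, while under section 2.5 the control arm receives balanced components with TEG-directed adjustment. Section 2.3 justifies the 4-hour phase with data from the earlier air medical plasma trial at the same institution: "Over 79% of the blood products transfused in the first 24 hours occurred in the first 4 hours" after admission.

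**The concern.** Presenting coagulopathy is of interest because it reflects the patient's state on reaching the trauma center, after the prehospital product and before the in-hospital one. If the arrival sample may be drawn at any time in the first 4 hours, the value can also reflect in-hospital products. Those differ by arm by design, so a late draw does more than add noise: it can change what the between-arm difference means.

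The later windows raise a second, separate problem. When two windows overlap, one draw can belong to either time point, and the documents give no assignment rule. Serial TEG and endothelial markers, which serve Specific Aim III, would then be grouped by labels that do not fix a time.

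There is also a conduct issue. A coordinator who draws at 3 hours complies with section 2.8 and misses the limit in section 6.5.2. Appendix 8 plans a table of protocol deviations by arm, so whether such a draw counts as a deviation needs one answer.

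**Working it through.** The plan states no figure of its own for this point, so there is none to reproduce. The check is interval arithmetic on the stated windows, taking arrival and admission as the same time origin (an assumption; sampling is timed from arrival, the transfusion figure from admission).

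**Inputs, in hours from arrival**

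| Item | Source | Interval |
|---|---|---|
| Arrival sample | 2.8 | 0 to 4 |
| First sample | 6.5.2 | 0 to 1 |
| 12-hour sample | 2.8 | 12 − 12 = 0 to 12 + 12 = 24 |
| 24-hour sample | 2.8 | 24 − 12 = 12 to 24 + 12 = 36 |
| In-hospital acute phase | 2.4 | 0 to 4 |

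Overlap = min(upper limits) − max(lower limits), and zero if negative.

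**1. The two arrival limits.** 4 / 1 = 4, a fourfold difference in the upper limit.

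**2. Arrival window against the acute phase.** min(4, 4) − max(0, 0) = 4 h, so the window covers all of the phase. A draw at the 4-hour limit follows over 79% of first-day products, in aggregate and if this trial resembles the earlier one. For earlier draws the documents give no figure. If products were given at an even rate over the 4 hours (an assumption), a draw at t hours would follow about 79% × t/4: 20% at 1 h, 40% at 2 h and 59% at 3 h. With the pace unknown, the share before a 1-hour draw could lie anywhere from none to all of that 79%.

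**3. The later windows.**
- 12 h against 24 h: min(24, 36) − max(0, 12) = 12 h, and 12/24 = 50% of each window.
- Arrival against 12 h: min(4, 24) − max(0, 0) = 4 h, and 4/4 = 100% of the arrival window.
- Arrival against 24 h: min(4, 36) − max(0, 12) = −8, so no overlap.

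A draw at 14 h therefore fits both the 12-hour and the 24-hour label, and a draw at 3 h fits both the arrival and the 12-hour label.

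**4. Can the planned data resolve it?** Section 2.8 records components in 6-hour totals. The first total covers 0 to 6 h, longer than the 0 to 4 h arrival window, so it cannot show what was given before an arrival draw. Section 6.4.6 requires start and stop times in the record for prehospital transfusion; no matching field for in-hospital products appears. Section 2.9 has no rule that uses actual draw time or products given before the draw.

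**5. Check of a replacement.** Windows of 0 to 4, above 4 to 18 and above 18 to 36 h do not overlap and cover 0 to 36 h. Draws at 11 h and 16 h, both allowed today, would fall in the same middle window, so the serial analysis has to use actual time if both are to count.

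**The case against.** The strongest reply is that the two limits need not conflict: section 2.8 may give a nominal time with a tolerance, and section 6.5.2 the working target inside it. Section 6.5.2 also concerns patients enrolled in transport, while section 5.1 allows enrolment by research staff after arrival in the emergency department, where a longer limit makes sense. This stands as a possible reading. Neither section says so, however, and the passages still have to be reconciled.

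A reader might infer that arrival samples will mostly be taken after treatment. The documents do not support that. The 79% figure is unpublished, comes from an earlier trial and applies only at the 4-hour limit; section 2.6 places research staff at arrival, which makes routine late draws less likely. Nor is there evidence that draw times will differ between arms: the sampling rule is the same in both. What differs by arm is the product given before a late draw.

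A reader might also infer that all coagulation results depend on the research draw. Only TEG is tied explicitly to the three time points; PT, PTT and INR could come from the initial clinical tests. In addition, the analysis section and the planned tables specify no coagulation comparison at all, so no prespecified analysis is known to be damaged.

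Finally, three sequential draws are clearly intended, so a 12-hour sample taken at arrival is a literal extreme. The 12 to 24 h overlap is not: draws in that range are well within the stated tolerance.

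**Conclusion.** The arrival sample has two limits that the protocol does not relate to each other. Under the longer one, a compliant sample can follow part or, at the extreme, most of the in-hospital transfusion and so may not measure presenting coagulopathy. The 12-hour and 24-hour windows share half their length and the arrival window lies inside the 12-hour one, with no rule to assign a draw.

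The effect is confined to TEG, coagulation tests where they come from this draw, and other arrival or mechanistic measures such as the endothelial markers and, if taken with this sample, arrival haptoglobin. The mortality outcome, the sample size and the stopping boundaries are untouched. How many samples would be late is unknown, so the size of any distortion cannot be stated. The point is still worth correcting: section 2.8 calls the mechanistic factors an essential objective, and the pilot is meant to inform a larger trial.

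**What to change.** 1. State one arrival rule in sections 2.8 and 6.5.2: for example, a target of within 1 hour, as section 6.5.2 already has it, with any later tolerance named as a tolerance. Say which rule applies to patients enrolled after arrival and which draws count as deviations.
2. Record the actual time of each draw and the in-hospital products given before it. A 1-hour limit alone does not ensure that a sample precedes in-hospital transfusion.
3. Keep all arrival samples in the randomised comparison. Add a sensitivity analysis limited to samples drawn within 1 hour or before the first in-hospital product. Restricting the main analysis in this way would select on a post-randomisation event, since how quickly a patient can be sampled may relate to severity or arm.
4. Assign samples to non-overlapping windows with lower bounds, for example 0 to 4 h, above 4 to 18 h and above 18 to 36 h. Analyse serial measures by actual time from arrival, so that two draws in one window are both used.

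The cost is wording in the protocol and analysis plan and one or two added data fields. Some samples change nominal label, and some patients may have two draws in one window and none in the next. Collection stays as flexible as it is now.

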7. COSTS AND PAYMENTS

Neither the participant, nor the insurance provider will be charged for the costs performed only for the purposes of this research study. Subject will be charged in the usual

manner for any procedures performed as part of your standard medical care (care the subject would receive even if they were not participating in this research study).


Clinical Protocol Appendix 1 Blood Product Maintenance

CENTER FOR EMERGENCY MEDICINE OF WESTERN PENNSYLVANIA, INC. STAT MEDEVAC

Blood Product Maintenance 1

Policy:

Base site blood products will be inspected daily for adequate temperature maintenance in the blood product storage refrigerator. Daily temperature checks will be documented in conjunction with the weekly circular graph temperature recording. Blood products will also be properly signed out of the blood refrigerator when indicated for missions and maintained at proper temperature until transfused or returned to the refrigerator.

2. Inventory/Expiration Tracking

Log

- a. All PRBC units must be logged on this sheet when received from the designated distribution point:
 - 1. STAT MedEvac 1 Washington Hospital Transfusion Services
 - I ab
 - 2. STAT MedEvac 2 Johnstown American Red Cross
 - 3. STAT MedEvac 3-UPMC Passavant Cranberry Blood Bank
 - 4. STAT MedEvac 4- UPMC McKeesport Transfusion Services
 - L
 - а h
 - 5. STAT MedEvac 5-Uniontown Hospital Blood Bank
 - 6. STAT MedEvac 6-Clarion Hospital Blood Bank
 - 7. STAT MedEvac 7-UPMC Horizon Transfusion Services L
 - а b
- 8. STAT MedEvac 8-UPMC Passavant Cranberry
- 9. STAT MedEvac 9-American Red Cross
- 10. STAT MedEvac 10-John Hopkins Hospital
- 11. STAT MedEvac 11 Altoona Hospital Blood Bank
- 12. STAT MedEvac 13-Baltimore American Red Cross
- 13. STAT MedEvac 14- UPMC Passavant Cranberry Blood В
 - а
- nk 14. STAT MedEvac 15-Washington Hospital Transfusion Services
 - Lab
 - 15. STAT MedEvac 16- UPMC Passavant Cranberry Blood В
 - а
 - nk
 - 16. STAT MedEvac 17-UPMC Hamot
 - 17. STAT MedEvac 18-Children's National Medical Center Blood
 - Bank
- b. Record the following information:

- 1. Unit Number
- 2. Date placed in service
- 3. Date unit will expire
- 4. Date unit is to be returned (minimum of 10 days prior to expiration date on blood products)
- 5. Initials of person confirming ABO type and placing units into service.
- 6. Disposition of units (transfused, wasted, or returned)
- 7. Location:- Note the receiving facility where patient receiving PRBCs transfusion was admitted.
- 8. Paperwork: Check that all appropriate paperwork is complet ed.
- 9. Comments: As needed, and list flight number associated with blood product transfusion.
- 10. Initials of person completing log regarding unit disposition.
- 3. Daily Checks / Shift Responsibilities: In order to prevent any problems with the recording chart to potentially go undetected for as long as 24 hours, check the chart midway through the shift for accurate documentation of current day and time every shift. Any problems should be corrected immediately and documented on the recording chart.
 - a. Temperature and Visual Inspection to be completed on every shift recording the following information on the Temperature Check and Visual Inspection Sheet: of
 - 1. Date
 - inspection
 - 2. Temperatures as indicated
 - a. Make sure temperature reading on recording chart corresponds with current day, time.
 - b. Make sure stylus is making contact with recording chart.
 - c. Notify Base Site Manager of any problems, i.e.: possibility of contamination, temperature not maintained between 1_{\circ} C to 6° C, inability to get recording chart to function properly.
 - 3. Refrigerator graph: Confirm accurate documentation of current day and time on the circular graph. Internal refrigerator temperatures and chart temperatures must both be within acceptable range (1-6° C) and agree with each other :t1°
 - Any gaps or fluctuations in temperature on a. recording have chart must explanation documented on chart followed by your initials.
 - b. A copy of all temperature documentation will be sent to the appropriate blood bank by the Base Site Coordinator or base representative.
 - 4. Contamination: Check each unit of blood for contamination and expiration date-i.e., if the red cell mass appears purple; if there is a zone of hemolysis: visible clots; if the plasma is murky; if plasma has a purple, brown, or red discoloration; if there are signs of leakage or inadequate sealing.
 - a. PRBC units that are questionable must be

quarantined and recorded as such in the comments section.

- b. Notify the appropriate blood bank immediately of quarantined blood.
- c. Exchange quarantined units for replacement units as soon as possible.
- 5. Confirm that blood is "0" negative or positive.
- 6. Confirm that blood is not due to expire by checking the inventory and expiration tracking log. If blood is to be returned, follow blood product return/transfer procedure.
- 7. Confirm ice or commercial ice packs are available for transport.
 - Comments as

needed

8.

9. Initials of person doing inspection.

b. Ensure refrigerator is clean and in working order.

3. Visual Inspection: Check appearance for contamination, clots,

discoloration, etc. List as satisfactory or unsatisfactory. 4. Initials: Your

initials.

- 5. Comments: Insert flight number and patient name if blood product was transfused.
- 7. Packing blood products for a mission
 - a. Blood products are to be taken on every mission.
 - b. Each unit should be in the plastic blood product bags
 - c. Place in the insulated cooler with commercial ice packs or ice and an appropriate thermometer. The units should be "sandwiched" between the ice using appropriate barriers to prevent the units from coming in direct contact with the ice.
 - d. If blood is not transfused, return it to the blood product refrigerator upon returning to base. Fill out remaining Columns 6-10 of Blood Tracking Log
- 8. Administration of blood products is to be carried out in strict accordance with STAT MedEvac Critical Care Protocols.
- 9. Documentation of transfusion
 - a. When a unit is transfused during a mission make sure the appropriate information is relayed to the receiving facility including type and unit number.
 - b. Fill out appropriate blood bank forms for transfused products per Central Blood Bank / American Red Cross instructions.
 - c. Upon return to the base, fill out the Blood Tracking Log for Columns 6-10 as
 - instructed.
- 10. Replacement of transfused blood products
 - a. Notify appropriate blood bank that you have transfused blood and specify the number of replacements needed.
 - i. Notify STAT Com and the Medical Director on call of any delay in receiving replacement units of blood and document the delay via special report.
- 11. Transfusion Complications
 - a. Notify the receiving facility of the patient's signs and symptoms immediately upon arrival.
 - b. Upon returning to base, an Adverse Reaction special report should be completed.

- 11. Blood refrigerator alarms
 - a. Monthly Check- High and low temperature alarms to be checked on the first of every month.
 - i. Remove blood from refrigerator and place on ice in cooler.
 - ii. Remove probe from glycerol solution and place the probe on ice. Temperature of probe will register below 1_c C within several minutes to activate alarm.
 - iii. The designated operator should call to advise of the Alarm. Activate the silence button on the blood product storage refrigerator after receiving phone call.
 - iv. Then place probe in tepid water to test high temperature alarm (>6°).
 - v. Again, the designated operator should call to confirm alarm activation. Activate the silence button on the blood product storage refrigerator after receiving phone call.
 - vi. Initial and note "Alarm Test" on Temperature Graph.
 - vii. Document "Alarms Checked/Operational or Non-Operational" in comment section of Daily Temperature Checks and Visual Inspection Logs.
 - viii. If alarms fail or no phone call is received from the designated operator keep blood on ice in cooler and notify the Base Site Manager immediately for guidance.
 - c. Alarm
 - Activation
 - i. The blood bank refrigerator will alarm any time the temperature in it rises above 6°C or below 1 0C or electrical power is shut *off* to the refrigerator.
 - ii. At the same time, the remote alarm will be activated at the Communications Specialist's switch board, the Communications Specialist will notify you by phone when the alarm activates.
 - iii. When alarm goes *off,* try to find any obvious causes, i.e., door is open to refrigerator, refrigerator is unplugged, circuit breaker is *off,* or circulating fan is not working.
 - iv. If cause cannot be found or corrected, removed blood and place it on ice in the cooler.
 - v. Notify the Base Site Manager immediately of problem. The Base Site Manager will instruct you as to what to do with the units of blood.
- 12. Quarterly Temperature Monitoring
 - a. Every quarter (March, June, September, and December) a verification of temperature maintenance of blood during emergency flights must be performed.
 - b. The following steps are to be performed when testing the temperatures:
 - 1. Store the bottle in your refrigerator along with the units of blood until needed.
 - 2. When packing units for an emergency, record the thermometer reading, time packed, date and initials on the card provided.
 - 3. Place the bottle into the cooler along with the blood.
 - 4. Assure that all the blood units and the bottle are covered with ice.

- 5. Upon return to base after flight, record the thermometer reading, time unpacked, date, and initials on the bottom of the card provided.
- 6. The acceptable range during transport is 1-10.
- c. A record of all results will be maintained at the base

